- ^b The Safety Follow-up Period will begin only if the patient discontinues from treatment early or completes the study and does not continue on ocrelizumab treatment (i.e., commercially available or from another source). Patients will be assessed in safety follow-up every 24 weeks for 48 weeks following the last infusion of ocrelizumab. After 48 weeks, if the peripheral blood B-cell count remains depleted, monitoring of the patient should continue at 24-week intervals until the B-cell count has returned to the baseline value or to the lower limit of the normal range, whichever is lower.
- ^c Biomarkers will be assessed via blood draws at Week 1 (pre-dose Day 1), Week 3 (pre-dose Day 15), and at timepoints noted from Weeks 12 through 52. Biomarkers will be assessed via LP in CSF before the first dose of ocrelizumab and from a second LP at Week 52 following the first dose of ocrelizumab.

Table 1 Study Cohorts and Overall Design

RMS Cohort		
	First LP	Second LP
Arm 1	Treatment baseline/Week 1	Week 12
Arm 2	Treatment baseline/Week 1	Week 24
Arm 3	Treatment baseline/Week 1	Week 52
Arm 4 (control arm)	Pre-treatment baseline/ Week -12	Treatment baseline/ Week 1
PPMS Cohort		
	First LP	Second LP
All PPMS patients	Treatment baseline/Week 1	Week 52

LP = lumbar puncture; PPMS = primary progressive multiple sclerosis; RMS = relapsing multiple sclerosis.

Note: Study Day 1 is the day of the first dose of study drug, and all relative day calculations are based on number of days from Study Day 1.

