- Known active bacterial, viral, fungal, mycobacterial infection, or other infection (including tuberculosis or atypical mycobacterial disease, but excluding fungal infection of nail beds) or any major episode of infection requiring hospitalization or treatment with IV antibiotics within 4 weeks prior to baseline visit or oral antibiotics within 2 weeks prior to baseline visit
- Any concomitant disease that may require chronic treatment with systemic corticosteroids or immunosuppressants during the course of the study
- Contraindications for, or intolerance to, oral or IV corticosteroids, including IV methylprednisolone, according to the country label, including:
 - Psychosis not yet controlled by a treatment
 - Hypersensitivity to any of the treatment drug constituents
- Contraindication for LP

- Previous treatment with B cell-targeted therapies (e.g., rituximab, ocrelizumab, atacicept, belimumab, or ofatumumab)
- Previous treatment with natalizumab (Tysabri[®]), alemtuzumab, anti-CD4 agents, cladribine, teriflunomide, cyclophosphamide, mitoxantrone, azathioprine, mycophenolate mofetil, cyclosporine, methotrexate, total body irradiation, or bone marrow transplantation
- Treatment with fingolimod (Gilenya[®]), dimethyl fumarate (Tecfidera[®]), or similar treatment within 6 months prior to enrollment
- Receipt of a live vaccine within 6 weeks prior to enrollment
 - Vaccinations before baseline: In rare cases where a live vaccine must be administered by the patient's physician, the screening period may need to be prolonged but cannot exceed 12 weeks.
- Systemic corticosteroid therapy within 4 weeks prior to baseline
 - The screening period may be extended (but cannot exceed 8 weeks) for patients who have used systemic corticosteroids for their MS before screening.
- Previous or concurrent treatment with any investigational agent or treatment with any experimental procedure for MS (e.g., treatment for chronic cerebrospinal venous insufficiency)
- Certain laboratory abnormalities or findings at screening, including the following:
 - Positive serum β -hCG
 - Positive for hepatitis B (hepatitis B surface antigen [HBsAg] positive or hepatitis B core antibody [total HBcAb] confirmed by positive viral DNA polymerase chain reaction [PCR]) or hepatitis C (HepCAb)
 - AST or ALT \geq 2.0 upper limit of normal (ULN)
 - Platelet count $<$ 100,000/ μ L ($< 100 \times 10^9/L$)
 - ANC $<$ $1.5 \times 10^3/\mu$ L
 - Abnormal lymphocyte count (*below LLN*)

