4.4.1 Permitted Therapy

Patients who use oral contraceptives, hormone-replacement therapy, or other maintenance therapy should continue their use.

- Anti-hypertensive medications
 - Since transient hypotension may occur during ocrelizumab infusion, the investigator may wish to withhold anti-hypertensive medications 12 hours prior to ocrelizumab infusion.
- IV or oral corticosteroids
 - *Patients who experience a relapse may receive treatment with IV or oral corticosteroids, if judged to be clinically appropriate by the investigator. Such patients should not discontinue treatment solely based on the occurrence of a relapse, unless the patient or investigator feels he or she has met the criteria for withdrawal (Section 4.6.3).*

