5.1.1.2 Infections

Infection is an identified risk associated with ocrelizumab treatment, predominantly involving mild to moderate respiratory tract infections. Non-disseminated herpes virus-associated infections, mostly mild to moderate, were also reported more frequently with ocrelizumab (approximately 5% to 6%, simplex and zoster) than with comparators (approximately 3%).

During the controlled period of the pivotal trials, the proportion of patients with serious infections was lower in RMS in the ocrelizumab group (1.3%) than in the interferon beta-1a group (2.9%); in PPMS, the proportion of patients with serious infections was similar in both groups: 6.7% in the placebo group compared with 6.2% in the ocrelizumab group.

Serious, opportunistic, and fatal infections have occurred in patients with lupus and rheumatoid arthritis (RA) treated with ocrelizumab in Phase III clinical trials. Data from completed studies regarding infection risks with ocrelizumab treatment in these patient populations are provided in the Ocrelizumab Investigator's Brochure.

No opportunistic infections were reported by any MS patient treated with ocrelizumab.

There were no reports of hepatitis B reactivation in MS patients treated with ocrelizumab, but it had been reported in one RA patient treated with ocrelizumab. HBV screening should be performed in all patients before initiation of treatment with ocrelizumab as per local guidelines. Patients with active hepatitis B virus should not be treated with ocrelizumab. Patients with positive serology should consult liver disease experts before the start of treatment and should be monitored and managed following local medical standards to prevent hepatitis B reactivation.

There were no reports of PML in patients treated with ocrelizumab. JCV infection resulting in PML has been observed in patients treated with anti-CD20 antibodies and other MS therapies and associated with risk factors (e.g., patient population, polytherapy with immunosuppressants). However, a risk of PML cannot be ruled out. Healthcare professionals should be alerted to the early signs and symptoms of PML, which can include any new onset or worsening of neurological signs or symptoms as these can be similar to an MS relapse. Please refer to [Appendix 6](#) for guidance for diagnosis of PML.

Delay ocrelizumab administration in patients with an active infection until the infection is resolved.

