2.2.2 Exploratory Endpoints

The exploratory endpoints for RMS Arm 4 include:

Change from first LP to second LP comparing Arm 4 to Arm 1 in:

- Levels of NfL in CSF
- Number of CD19 + B cells in CSF

- Number of CD3 + T cells in CSF
- Levels of NfL in blood
- Number of CD19 + B cells in blood
- Number of CD3 + T cells in blood

The exploratory endpoints for the PPMS cohort are:

- Change in levels of NfL in CSF from treatment baseline to post-treatment
- Change in number of CD19 + B cells in CSF from treatment baseline to post-treatment
- Change in number of CD3+T cells in CSF from treatment baseline to post-treatment

For both RMS and PPMS cohorts, other exploratory endpoints include the impact of ocrelizumab treatment on other CSF biomarkers, blood biomarkers and MRI biomarkers listed in this section.

Change from treatment baseline in CSF biomarkers:

- %CD19+ B cell
- %CD3+ T cell
- %CD4+ (CD3+)
- CD4+CD3+ number
- %CD4- (CD3+)
- CD4-CD3+ number
- %IgD+CD27+ (CD19+)
- IgD+CD27+CD19+ number
- %IgD+CD27- (CD19+)
- IgD+CD27-CD19+ number
- %IgD-CD27- (CD19+)
- IgD-CD27-CD19+ number
- %IgD-CD27+ (CD19+)
- IgD-CD27+CD19+ number
- %CD138+CD38+ (IgD-CD27+)
- CD138+CD38+IgD-CD27+CD19+ number
- %CD138-CD38- (IgD-CD27+)
- CD138-CD38-IgD CD27+CD19+ number
- %CD138-CD38+ (IgD-CD27+)
- CD138-CD38+IgD-CD27+CD19+ number
- %CD38+ (IgD+CD27-)
- CD38+IgD+CD27-CD19+ number
- IgG
- IgM
- CXCL13
- CCL19
- Strem2

- YKL40
- IL-6

Change from treatment baseline in Blood biomarkers:

- %CD19+ B cell
- %CD3+ T cell
- CD3+ T cell number
- CD4+T cell number
- CD8+T cell number
- CD19+ B cell number
- CD56+CD16+ NK cell number
- CD4/CD8 Ratio
- NfL
- CXCL13
- IL-6

MRI biomarkers:

- Mean number of T1 Gd-enhanced lesions
- Mean number of new and/or enlarging T2 lesions
- Mean T2 lesion volume
- Mean Regional or total brain volume
- Mean number of leptomeningeal-enhancing regions

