4.4 EFFICACY ANALYSIS

All biomarker assessments (scheduled or unscheduled) will be summarized after applying visit windows. Summary of the visit windowing rules can be found in Appendix 2. See Module 3 for full visit window specifications. If multiple values of the same parameter occur within the same time window for blood biomarkers

Ocrelizumab—Genentech, Inc.

15/Statistical Analysis Plan ML29966

or regular lab values, the worst value for that parameter will be presented in the summary table. If multiple MRI scans occur within the same time window, the scan closest to the scheduled visit date will be included in the analysis.

All summaries will be done based on the ITT population and summaries will be provided by the actual arm, as determined by the actual timing of 2nd LP:

For patients randomized to Arm 1-3,

If the second LP date is missing then patient is included in the arm where originally randomized to;

Else:

Study Day of second LP (= date of the 2nd LP – 1st infusion start date +1)	Treatment Arm
≤126	Arm 1
127-266	Arm 2
≥267	Arm 3

Patients randomized to Arm 4 will be summarized as Arm 4 regardless of the timing of 2nd LP.

Unless otherwise specified and where appropriate, statistical tests, if any, will be performed at the two-sided 5% significance level. Corresponding 95% confidence intervals will be presented as appropriate. No corrections for multiple testing will be applied.

For biomarkers measured below the lower limit of quantification (LLOQ), numeric values will be imputed using half of the LLOQ.

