4.4.2 Exploratory Endpoints

4.4.2.1 Summaries of Exploratory Endpoints Over Time

For RMS patients in Arm 4, values at pre-treatment baseline and treatment baseline, and change and percent change from treatment baseline to post-baseline visits will be summarized.

For RMS patients in arms 1-3 and PPMS patient arm, CSF biomarker endpoints, blood biomarker endpoints and MRI biomarker endpoints stated in Section 2.2.2 will be summarized over time following the same rule as the primary efficacy endpoint, as stated in Section 4.4.1. The median (IQR) value of CSF and blood biomarkers at pre-treatment baseline, treatment baseline and post-baseline visits will be plotted over time and color coded by each arm. Scatter points of data will be laid over the median (IQR) plot for blood NfL level, CD19+ B cell and CD3+ T cell numbers.

Mean (SD) of MRI biomarker endpoints will be summarized over time.

For blood biomarkers, patient arms will also be pooled to look at the effect of ocrelizumab over time.

4.4.2.2 Comparison between Arm 1 and Arm 4

For patients in Arm 4, changes from pre-treatment baseline to treatment baseline will be compared to Arm 1 change from treatment baseline to Week 12 through an ANCOVA model adjusting for baseline DMT status (DMT naïve vs. DMT experienced) and baseline biomarker level for the following endpoints:

- CSF CD19+ B cell, CD3+ T cell and NfL
- Blood CD19+ B cell, CD3+ T cell and NfL

If data are highly skewed, ANCOVA model will be based on percent changes.

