Week 192	1344	>=1,261 and <=1,428	Window is from Week 180+1 day to Week 204
Week 216	1512	>=1,429 and <=1,596	Window is from Week 204+1 day to Week 228
Week 240	1680	>=1,597	Window is Week 228+1 day to end of LTE

Visit window for MRI biomarkers (Arm 1-4 & PPMS):

Report Visit Label	Nominal study days (from baseline)	Visit window (in terms of study days from baseline)	Notes
Week -12 (Arm 4)	-84	<=-28	
Baseline (Arm 4)	1	>-28 and <=1	Give a 4-week window for baseline visit

Baseline (Arm 1-3 & PPMS)	1	<=1	
Week 12	84	2<= and <=126	Window is from Day 2 until Week 18
Week 24	168	127<= and <=266	Window is from Week 18+1 day until Week 38
Week 52	364	267 - < LTE Day 1 (if entered LTE) 267 – patient end of main study date (if not entered LTE)	Window is from Week 38 +1 day
Week 96	672	LTE Day 1 - <=840	Window is from LTE Day 1 to Week 120
Week 144	1008	>=841 and <=1,176	Window is from Week 120+1 day to Week 168
Week 192	1344	>=1,177 and <=1,512	Window is from Week 168+1 day to Week 216
Week 240	1680	>=1,513	Window is from Week 216+1 day to end of LTE

*Early withdrawal, B cell monitoring and safety follow up 1 and 2 excluded from windowing

Visit window for CSF Biomarkers (Arm 1-4 & PPMS):

Report Visit Label	Nominal study days (from baseline)	Visit window (in terms of study days from baseline)	Notes
Week -12 (Arm 4)	-84	< -14	
Baseline (Arm 4)	1	-14 - 1	Give a 2-week window for baseline visit
Baseline (All patients except Arm 4)	1	<=1	
Week 12 (All patients)	84	2 - 126	
Week 24 (All patients)	168	127-266	
Week 52 (All patients)	364	267 - < LTE Day 1 (if entered LTE) 267 – patient end of main study date (if not entered LTE)	
Week 144 (All patients)	1,008	LTE Day 1 - <=1,344	Window is from LTE Day 1 to Week 192

Week 240 (All patients)	1,680	$\geq 1,345$	Window is from Week 192+1 day to end of LTE
-------------------------	-------	--------------	---

Visit window for EDSS:

Report Visit Label	Nominal study days (from baseline)	Visit window (in terms of study days from baseline)	Notes
Screening (Arm 4)	N/A	≤ -97	
Screening (Arm 1-3 & PPMS)	N/A	≤ -13	
Week -12 Pre-Baseline (Arm 4)	-84	$-97 - \leq -14$	Give a 2-week window for baseline visit
Baseline (Arm 1-3 & PPMS)	1	$-13 - \leq 1$	Give a 2-week window for baseline visit
Baseline (Arm 4)	1	$-14 - \leq 1$	Give a 2-week window for baseline visit
Week 12 (All Patients)	84	$2 \leq \text{and} \leq 126$	Window is from Day 2 until Week 18
Week 24 (All Patients)	168	$127 \leq \text{and} \leq 210$	

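### SAP Appendix 2 counts Arm 4's second lumbar puncture as treatment baseline only within 14 days of first dose, so a long dosing delay empties the control value that SAP 2.2.2 defines by puncture order

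*SAP*

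**What the plan says.** **Windows.** For CSF, SAP Appendix 2 gives Arm 4 two pre-dose windows. Week -12 takes any day before -14, with no lower limit. Baseline takes Day -14 to Day 1, with the note "Give a 2-week window for baseline visit". All other patients have one pre-dose window, Day 1 or earlier. Blood biomarkers use the same Day -14 cut for Arm 4. The Arm 4 MRI baseline window is wider, from after Day -28 to Day 1.

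**Anchor.** The note to Protocol Table 1 makes the first dose Study Day 1, and "all relative day calculations are based on number of days from Study Day 1". SAP 4.4 also counts from the infusion ("1st infusion start date +1"), in a formula written for Arms 1-3.

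**Handling.** SAP 4.4 windows every biomarker assessment. For several values in one window it has a rule for blood and laboratory data (worst value) and for MRI (closest to schedule), but none for CSF. SAP 4.7 rules out imputation for efficacy analyses.

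**The contrast, defined twice.** SAP 2.2.2 goes by LP order: "Change from first LP to second LP comparing Arm 4 to Arm 1 in" three CSF and three blood markers. SAP 4.4.2.2 goes by visit label: "changes from pre-treatment baseline to treatment baseline will be compared to Arm 1 change from treatment baseline to Week 12".

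**Conduct.** Protocol Appendix 2 schedules the Arm 4 LPs at Week -12 and at Week 1 before dosing. The LP, then the MRI, may come up to 7 business days before the infusion. Entry criteria are marked for review at screening, Week -12 and Week 1. The protocol's Infections section (5.1.1.2) says: "Delay ocrelizumab administration in patients with an active infection until the infection is resolved". Section 4.1.2 excludes "Systemic corticosteroid therapy within 4 weeks prior to baseline" without saying which of Arm 4's two baselines is meant. Section 4.4.1 adds: "Patients who experience a relapse may receive treatment with IV or oral corticosteroids, if judged to be clinically appropriate by the investigator".

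**The concern.** Arm 4 is the study's only control. Protocol 3.1 gives it the task of showing how biomarkers move without ocrelizumab. For that purpose the informative pair is the two LPs about 12 weeks apart, and when the first infusion happens afterwards is irrelevant.

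The Appendix 2 rule nevertheless ties the second LP's label to the infusion date. A patient can have both LPs on schedule and still contribute no control change because dosing was later put off. The same delay leaves an Arm 1 baseline intact. Any loss is therefore one-sided and follows something that happened to the patient during the wait. SAP 4.4 keeps such a patient in Arm 4, so the loss would appear only as a missing value.

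**Working it through.** **Plan's own figures.** The plan gives no number for delayed first doses. Two of its figures bear on size.
- Arm 4 has 15 patients, 16 enrolled (15 x 1.10 = 16.5).
- The SD of NfL change reproduces: sqrt(780² + 310² - 2 x 0.6 x 780 x 310) = 643.7 pg/mL, against 643 stated. With a change of 860 - 602 = 258 pg/mL, the exact paired t-test has power 0.802 at the stated n of 51.

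**Step 1: the gap that relabels the LP.** Let g be the calendar days from second LP to first infusion.
- With no Day 0, the LP is on Day -g. It becomes Week -12 when -g < -14, so g is 15 or more.
- With the SAP 4.4 formula, the LP is on Day -g + 1. It becomes Week -12 when -g + 1 < -14, so g is 16 or more.

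**Step 2: compliant timing.** Holidays aside, 7 business days is 9 calendar days for an LP on Monday to Wednesday and 11 for Thursday or Friday. Compliant samples always stay baseline.

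**Step 3: the slip needed.**
- LP at the earliest allowed time: 15 - 11 = 4 days to 16 - 9 = 7 days.
- LP on the planned dosing day: 15 or 16 days. This is not the expected pattern, because the LP should precede the MRI and the MRI needs 2 business days of quality checking before dosing.

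**Step 4: what is lost past the cut.**
- Both LPs sit in Week -12, and no CSF rule chooses between them.
- Treatment baseline is empty, so the 4.4.2.2 change has no second value. The Arm 4 change from treatment baseline to later visits (4.4.2.1) and the Arm 4 association of CSF change with MRI change (4.4.2.3) fail for the same reason.
- An MRI from the same visit at Day -15 to -27 is still labelled baseline, so LP and scan get different labels.
- An Arm 1 first LP on those days is still baseline.

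**Step 5: how many patients.** The documents do not allow this to be computed. As an illustration, take rates from other studies (Protocol 1.2.1) and count events starting in a gap of 9 to 11 days among 16 patients: 16 x rate x days / 365.25.
- Infection: 52.4% of interferon patients over 96 weeks implies -ln(1 - 0.524) / (96 x 7 / 365.25) = 0.40 per year for a first infection. Expected: 0.16 to 0.19.
- Relapse at 0.364 per year (interferon): 0.14 to 0.18. At 0.637 (placebo): 0.25 to 0.31.
- Together: from 0.16 + 0.14 = 0.30 to 0.19 + 0.31 = 0.50 patients, before asking whether the event delays dosing long enough.

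**Step 6: what one loss does.** Assume SD 643 in both arms, 15 in Arm 1 and an unadjusted comparison.
- Precision: SE = 643 x sqrt(1/15 + 1/n) is 234.8 with n = 15 in Arm 4 and 238.9 with 14. The difference detectable with 80% power, (1.960 + 0.842) x SE, goes from 658 to 669 pg/mL. Power for 258 pg/mL goes from 0.195 to 0.189.
- Selection: leaving out one of 15 patients, whose change differs by d from the mean of the other 14, moves the mean by d/15. For d = 643 (one SD) that is 43 pg/mL.

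**The case against.** The strongest defence is that compliant timing never triggers the rule. If a problem is known before the second LP, the LP can move with the dose. Loss needs a sequence: LP done, then an event or a late-recognised exclusion, then a slip past the cut. Arm 4 has two pre-dose LPs and needs some separator, so a lower bound is not wrong in itself. SAP 2.2.2 already goes by LP order. Appendix 2 is described as a summary, with full rules in Module 3, which was not available and may hold a safeguard. The contrast is exploratory and Arm 4 was not sized statistically. All of this stands and limits the size of the point. It does not remove the conflict between 2.2.2 and 4.4.2.2, or the missing CSF rule.

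A reader might infer that relapsing patients are the ones most likely to be lost. The documents do not support that.
- Protocol Appendix 2 ties the steroid-related screening extension to Week -12.
- Protocol 4.4.2 exempts systemic corticosteroids from its pre-dose restriction on MS therapies.
- Nothing says that a relapse delays the first dose. Active infection has an explicit delay rule.
- The Week 1 criteria review leaves it unclear whether the steroid look-back applies again.

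A reader might also count every relapse in the last 4 weeks before Week 1 as a lost patient: 1 - exp(-rate x 4/52) = 2.8% and 4.8%, times 16 = 0.44 and 0.77 patients, with a 36% to 54% chance of at least one. That is the chance of a relapse, not of relabelling. Suppose a 4-week look-back did apply again at Week 1 and the LP was on the planned dosing day. Steroids that ended more than 14 days earlier would then need a delay under 14 days, and the LP would stay baseline.

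**Conclusion.** The point holds in limited form. Read literally, Appendix 2 misclassifies an on-schedule second LP in Arm 4 once the gap to first dose reaches 15 or 16 days, and the change in SAP 4.4.2.2 is then lost although SAP 2.2.2 would keep it. Not every delay does this: the gap must exceed the protocol's 9 to 11 calendar days.

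The expected number affected is probably under one patient. That rests on outside rates at constant hazard, and it omits repeat infections, laboratory findings and logistics. One loss would be 1/15, or about 7%, of the control arm. The cost in precision is negligible. The cost in selection is unknown in direction, one-sided, and about 43 pg/mL per SD by which the lost patient differs from the rest.

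The conclusion assumes that Module 3 repeats the Appendix 2 windows. It also assumes that the 7-business-day allowance still applies: it comes from protocol version 4, while the SAP reproduces the version 5 synopsis.

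**What to change.** - In SAP Appendix 2 and Module 3, assign Arm 4 CSF and the paired blood sample by scheduled LP order: first scheduled pre-dose LP as pre-treatment baseline, second as treatment baseline, whatever the gap to first infusion.
- Exclude unscheduled relapse LPs from this count. Protocol 3.1 offers one at any relapse during the study, whereas Protocol Appendix 2 limits it in Arm 4 to after both LPs. Without the exclusion, a relapse sample could be taken as treatment baseline.
- List actual inter-LP and LP-to-dose intervals for Arm 4.
- Add a rule for several CSF samples in one window.
- Word 4.4.2.2 to match 2.2.2.
- Reconcile Protocol 4.1.2 with the Week 1 criteria review and the screening-window footnote in Protocol Appendix 2, so that sites know which Arm 4 baseline each look-back refers to.

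The cost is one derivation and a few sentences, with no new data. The downside is that some Arm 4 intervals will differ from 12 weeks, which the listing makes visible.
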